5. ANALYSIS SETS

5.1. Definition

5.1.1. Enrolled Set

The Enrolled Set will include all the subjects for whom valid signed informed consent form is available

5.1.2. Randomized Set

The Randomized Set will include all the subjects for whom valid signed informed consent form is available and treatment is allocated.

5.1.3. Exposed Set (ES)*

The Exposed set (ES) will include all subjects with at least one vaccine administration documented:

- The ES for analysis of solicited adverse events will include all subjects with at least one documented administered vaccine.
- The ES for analysis of unsolicited AEs, SAEs and pIMDs will include all subjects with at least one vaccine administered.
- The ES for analysis of immunogenicity will include vaccinated subjects for whom immunogenicity data are available.

The ES analysis will be performed per treatment actually administered (at Dose 1).

5.1.4. Per-protocol set (PPS)* for immunogenicity

The Per-protocol set for immunogenicity will include all evaluable subjects:

- who meet all eligibility criteria,
- who comply with the procedures and intervals allowed for the analysis,
- who do not meet any of the criteria for elimination during the study,
- for whom data concerning immunogenicity endpoint measures are available.

17

^{*} Note that in order to align to ICH and cDISC terminology the Total Vaccinated Cohort and the Per- Protocol cohort have been renamed Exposed Set (ES) and Per-Protocol Set (PPS) respectively.

204487 (ZOSTER-059 PRI) Statistical Analysis Plan Amendment 3

The intervals allowed for the inclusion in the *PPS for immunogenicity* are defined as follows:

	Group	Interval	Allowed interval for PPS analysis of immunogenicity
Interval between	Co-Ad	HZ/su (Dose 1) – HZ/su (Dose 2)	49-83 Days
vaccinations	Control	Prevenar13 (Dose 1) – HZ/su (Dose 2)	>= 60 days*
	Control	HZ/su (Dose 2) – HZ/su (Dose 3)	49-83 Days
Interval between vaccination and blood sample	Co-Ad	Prevenar13 (Dose 1) – Visit Month 1 for BS	28-48 Days*
taken	Co-Ad	HZ/su (Dose 2) – Visit Month 3 for BS	28-48 days*
	Control	Prevenar13 (Dose 1) – Visit Month 1 for BS	28-48 Days*
	Control	HZ/su (Dose 3)– Visit Month 5 for BS	28-48 days*

BS= blood sampling taken; *please note these intervals differ from protocol amendment 2 Table 8 and 9 to increase the number of evaluable subjects while not compromising the interpretation of immunogenicity data

5.2. Criteria for eliminating data from Analysis Sets

Elimination codes are used to identify subjects to be eliminated from analysis. Detail is provided below for each set.

5.2.1. Elimination from Enrolled Set

Code 900 (invalid informed consent or fraud data) will be used for identifying subjects eliminated from Enrolled Set.

5.2.2. Elimination from Randomized Set

Code 900 (invalid informed consent or fraud data) and code 1010 (vaccine number not allocated) will be used for identifying subjects eliminated from Randomized Set.

5.2.3. Elimination from Exposed Set (ES)

Code 1030 (Study vaccine not administered at all), code 1010 (vaccine number not allocated) and code 900 (invalid informed consent or fraud data) will be used for identifying subjects eliminated from ES.

204487 (ZOSTER-059 PRI) Statistical Analysis Plan Amendment 3

5.2.4. Elimination from Per-protocol analysis Set (PPS)

A subject will be excluded from the PPS analysis under the following conditions:

Code	Condition under which the code is used	Visit (timepoints) where the code is applicable	Applicable for analysis set
900	Invalid informed consent or fraudulent data. Subjects excluded from all stat analysis Note: Subjects receiving a code 900 should not receive any other elimination codes.	All	All
1010	Vaccine number not allocated Note: Subjects receiving a code 1010 should not receive any other elimination codes	Day 1	Randomized Set, ES, PPS
1030	Study vaccine not administered AT ALL but subject number allocated Note: Subjects receiving a code 1030 should not receive any other elimination codes	Day 1	ES, PPS
1040*	Administration of concomitant vaccine(s) forbidden in the protocol Comment: Co-Ad group: From 30 days before 1st vaccination up to Month 3 blood sampling Control group: From 30 days before 1st vaccination up to Month 5 blood sampling	Co-Ad group: Day -30 to Month 3 Control group: Day -30 to Month 5	PPS
1050	Randomization failure (subject not randomized in the correct group) Comment: To check for manual randomisation, treatment not compatible with one assigned by SBIR	Day 1	PPS
1070	 Side, site or route of study vaccine administration wrong or unknown Administration not according to protocol for reason specified by the investigator, other than side, site and route Wrong replacement or study vaccine administered (not compatible with the vaccine regimen associated to the treatment number) Administered study vaccine reported as being the correct one but is not compatible with the vaccine regimen associated to the treatment number. 	Co-Ad group – Day 1, Month 2 Control group – Day 1, Month 2, Month 4	PPS
1080	Vaccine has been administered (effective treatment number) despite a temperature deviation qualified by Status QA GMP NON Use	Co-Ad group – Day 1, Month 2 Control group – Day 1, Month 2, Month 4	PPS
1090	Expired vaccine administered	Co-Ad group – Day 1, Month 2 Control group – Day 1, Month 2, Month 4	PPS
2010	Protocol violation (inclusion/exclusion criteria)	Day 1	PPS
2040*	Administration of any medication forbidden by the protocol Co-Ad group: From 1st vaccination up to Month 3 blood sampling Control group: From 1st vaccination up to Month 5 blood sampling	Co-Ad group – Day 1 up to Month 3 Control group – Day 1 up to Month 5	PPS

204487 (ZOSTER-059 PRI) Statistical Analysis Plan Amendment 3

	Statistical Analysis Plan Amendment				
Code	Condition under which the code is used	Visit (timepoints) where the code is applicable	Applicable for analysis set		
2050*	Underlying medical condition forbidden by the protocol Co-Ad group: From 1st vaccination up to Month 3 blood sampling	Co-Ad group – Day 1 up to Month 3	PPS		
	Control group: From 1st vaccination up to Month 5 blood sampling	Control group – Day 1 up to Month 5			
2060*	Concomitant infection related to the vaccine which may influence immune response Co-Ad group: From 1st vaccination up to Month 3 blood sampling	Co-Ad group – Day 1 up to Month 3 Control group – Day 1 up	PPS		
	Control group: From 1st vaccination up to Month 5 blood sampling	to Month 5			
2070*	Concomitant infection not related to the vaccine which may influence immune response Comment:	Co-Ad group – Day 1 up to Month 3	PPS		
	Co-Ad group: From 1st vaccination up to Month 3 blood sampling Control group: From 1st vaccination up to Month 5 blood sampling	Control group – Day 1 up to Month 5			
2080	Subjects did not comply with vaccination schedule (dates of vaccination not corresponding to adapted protocol intervals provided in SAP or unknown	Co-Ad group: Day 1, Month 2	PPS		
	vaccination dates) Comment: Co-Ad group: DOSE 1 – DOSE 2 Control group: DOSE 1 – DOSE 2 DOSE 2 – DOSE 3	Control group: Day 1, Month 2, Month 4			
2090	Subjects did not comply with blood sample schedule (dates of BS not corresponding to adapted protocol intervals provided in SAP or unknown BS/vaccination	Co-Ad group: Month 1, Month 3	PPS		
	dates) Comment: Co-Ad group: DOSE 1 – MONTH 1 BS	Control group: Month 1, Month 5			
	DOSE 2 – MONTH 1 BS Control group: DOSE 1 – MONTH 1 BS DOSE 3 – MONTH 5 BS				
2100	Serological results not available post-vaccination (including lost samples, blood sample not done, unable to test, absence of parallelism). Please specify the applicable rule: elimination code if ALL are missing for a subject Comment:	Co-Ad – Month 1, Month 3 Control – Month 1, Month 5	PPS		
	Co-Ad group: Check for availability of anti-gE serological result at Month 3 and for pneumococcal serological results at Month 1 Control group: Check for availability of anti-gE serological result at Month 5 and for pneumococcal serological results at Month 1				
2120	Obvious incoherence or abnormality or error in data (incoherence between CRF and results, wrong labelling) Comment: Co-Ad group: Check for above condition on anti-gE	Co-Ad – Month 1, Month 3 Control – Month 1, Month 5	PPS		
	serological result at Month 3 and on pneumococcal serological results at Month 1				

204487 (ZOSTER-059 PRI) Statistical Analysis Plan Amendment 3

Code	Condition under which the code is used	Visit (timepoints) where the code is applicable	Applicable for analysis set
	Control group: Check for above condition on anti-gE serological result at Month 5 and on pneumococcal serological results at Month 1		
2500	Incomplete vaccination course. Comment: The subject should receive one dose of Prevenar 13 vaccine and 2 doses of Hz/su vaccine	Co-Ad – Day 1, Month 2 Control – Day 1, Month 2, Month 4	PPS

BS = Blood sample

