1. DOCUMENT HISTORY

Date	Description	Protocol
		Version
13 APR	First Version	Amendment 2:
2018		30 JAN 2018
11 JUN	Amendment 1 - Summary of changes as below:	Amendment 2:
2019	- As per new process applicable, the front page has been	30 JAN 2018
	modified to remove the names of all the contributing author	
	and reviewers. Also, sign-off is only required to be done by	
	Lead Statistician	
	- Updated LLOQ and newly calculated ULOQ for the 13	
	pneumococcal serotypes tested by MOPA have been added	
	and accordingly analysis of immunogenicity section has been	
	updated.	
	- Consort table have been added for subject disposition.	
	- Additional tables for fatal serious adverse events (SAEs) and	
	grade 3 non-serious unsolicited adverse events (AEs) have	
	been added.	
	- The term "symptom" has been changed to "adverse event	
	(AE)" in endpoints, table titles and content for solicited AEs,	
	unsolicited AEs, SAEs, and potential immune mediated	
	diseases (pIMDs).	
	- Table 'Summary of temperature value by half degree	
	increment reported during the 7-day (Days 1-7) post-	
	vaccination following each dose' has been removed	
	- Sequence of analysis has been updated	
	- Inclusion of Enrolled and Randomized Set definition	
	- Code 1500 in elimination codes has been removed and added	
	under code 1070. Also, mandatory columns have been added	
	in the elimination table under 'Elimination from PPS section.	
20-	Amendment 2 - Summary of changes as below:	Amendment 2:
NOV-	- The active phase analysis has been removed as a request for	30 JAN 2018
2019	a CTRS posting extension has been submitted to NIH;	
	complete CTRS posting will be done at Last Subject Last Visit	
	(LSLV) + 12 months rather than Primary Completion Date	
	(PCD) +12 months as previously planned	
	- Titles and Footnotes of selected templates have been updated	
	following the Dry run kick-off meeting	
	- Two new safety templates have been added (Templates 49	
	and 50)	
23-	Amendment 3 – Summary of changes: -	Amendment
NOV-	Few templates have been edited for better presentation	2: 30 JAN
2020	Removal of template for vaccine response table with only one	2018
	group for primary objective assessment; Addition of separate	
	template for anti-gE seropositivity rate and GMC, list of PT	
	codes to identify suspected HZ episode	

204487 (ZOSTER-059 PRI) Statistical Analysis Plan Amendment 3

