Template 9 Deviations from specifications for age and intervals between study visits for Co-Ad group <Exposed Set>

		, ,		Dose:1- Dose:2	Dose:2-PII (M3)		Dose:2- PHC (M14)	
Group		Protocol from ≥ 50	Protocol from 30 to		Protocol from 49 to 83	Protocol from 30 to	Adapted from 28 to 48	Protocol from 335
		years	42 days	days	days	48 days	days	to 395 days
Co-Ad	N							
	n							
	%							
	range							

Co-Ad = Dose 1: Prevenar 13+ HZ/su, Dose 2: HZ/su

Adapted = interval used for defining PPS for immunogenicity

N = total number of subjects with available results

n/% = number / percentage of subjects with results outside of the interval

range = minimum-maximum for age and intervals

PI (M1) = Blood sample at Month 1, post-vaccination Dose 1; PII (M3) = Blood sample at Month 3, post-vaccination

Dose 2; PHC (M14) = Phone Contact MONTH 14

204487 (ZOSTER-059 PRI) Statistical Analysis Plan Amendment 3

Template 10 Deviations from specifications for age and intervals between study visits - for Control group <Exposed Set>

		Age	Dose:1-PI(M1)	Dose:1-Do	se:2	Dose:2- Dose:3	Dose:3-PII	` ,	Dose:3- PHONE CONT M16
Group		Protocol	Protocol	Adapted	Protocol	Adapted	Protocol	Protocol	Adapted	Protocol
		from ≥ 50	from 30 to	from 28 to	from 60 to	≥ 60	from 49 to	from 30 to	from 28 to	from 335 to
		years	42 days	48 days	83 days	days	83 days	48 days	48 days	395 days
Control	N			_			_	-	-	•
	n									
	%									
	range									

Control = Dose 1: Prevenar 13, Dose 2: HZ/su, Dose 3: HZ/su

Adapted = interval used for defining the **PPS for immunogenicity**

N = total number of subjects with available results

n/% = number / percentage of subjects with results outside of the interval

range = minimum-maximum for age and intervals

PI(M1) = Blood sample at Month 1, post-vaccination Dose 1; PIII(M5) = Blood sample at Month 5, post-vaccination

Dose 3; PHC (M16) = Phone Contact Month 16

Template 11 Summary of demographic characteristics <Exposed Set, PPS for immunogenicity>

	<each group=""> N=XXXX</each>			<each group=""> N=XXXX</each>		otal XXXX
	Value or n	%	Value or n	%	Value or n	%
Age in Years at <timepoint></timepoint>						
N with data	xxx		XXX		XXX	
Mean	XXX.X		XXX.X		XXX.X	
SD	XXX.X		XXX.X		XXX.X	
Median	xxx.x		XXX.X		XXX.X	
Minimum	xxx		XXX		XXX	
Maximum	XXX		XXX		XXX	
Gender						
<each gender=""></each>	xxx	XX.X	XXX	XX.X	XXX	XX.X
	XXX	XX.X	XXX	XX.X	XXX	XX.X
Ethnicity						
<each ethnicity=""></each>	xxx	XX.X	XXX	XX.X	XXX	XX.X
	xxx	XX.X	xxx	XX.X	XXX	XX.X

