	Statistical Analysis Plan Amendment 2			
Code	Condition under which the code is used	Visit (timepoints) where the code is applicable	Applicable for analysis set	
2050*	Underlying medical condition forbidden by the protocol Co-Ad group: From 1st vaccination up to Month 3 blood sampling	Co-Ad group – Day 1 up to Month 3	PPS	
	Control group: From 1st vaccination up to Month 5 blood sampling	Control group – Day 1 up to Month 5		
2060*	Concomitant infection related to the vaccine which may influence immune response Co-Ad group: From 1st vaccination up to Month 3 blood sampling	Co-Ad group – Day 1 up to Month 3 Control group – Day 1 up	PPS	
	Control group: From 1st vaccination up to Month 5 blood sampling	to Month 5		
2070*	Concomitant infection not related to the vaccine which may influence immune response Comment:	Co-Ad group – Day 1 up to Month 3	PPS	
	Co-Ad group: From 1st vaccination up to Month 3 blood sampling Control group: From 1st vaccination up to Month 5 blood sampling	Control group – Day 1 up to Month 5		
2080	Subjects did not comply with vaccination schedule (dates of vaccination not corresponding to adapted protocol intervals provided in SAP or unknown	Co-Ad group: Day 1, Month 2	PPS	
	vaccination dates) Comment: Co-Ad group: DOSE 1 – DOSE 2 Control group: DOSE 1 – DOSE 2 DOSE 2 – DOSE 3	Control group: Day 1, Month 2, Month 4		
2090	Subjects did not comply with blood sample schedule (dates of BS not corresponding to adapted protocol intervals provided in SAP or unknown BS/vaccination	Co-Ad group: Month 1, Month 3	PPS	
	dates) Comment: Co-Ad group: DOSE 1 – MONTH 1 BS	Control group: Month 1, Month 5		
	DOSE 2 – MONTH 3 BS Control group: DOSE 1 – MONTH 1 BS DOSE 3 – MONTH 5 BS			
2100	Serological results not available post-vaccination (including lost samples, blood sample not done, unable to test, absence of parallelism). Please specify the applicable rule: elimination code if ALL are missing for a subject Comment:	Co-Ad – Month 1, Month 3 Control – Month 1, Month 5	PPS	
	Co-Ad group: Check for availability of anti-gE serological result at Month 3 and for pneumococcal serological results at Month 1 Control group: Check for availability of anti-gE serological result at Month 5 and for pneumococcal serological results at Month 1			

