		Statistical Analysis Pla	
Code	Condition under which the code is used	Visit (timepoints) where the code is applicable	Applicable for analysis set
2050*	Underlying medical condition forbidden by the protocol Co-Ad group: From 1st vaccination up to Month 3 blood sampling	Co-Ad group – Day 1 up to Month 3	PPS
	Control group: From 1 st vaccination up to Month 5 blood sampling	Control group – Day 1 up to Month 5	
2060*	Concomitant infection related to the vaccine which may influence immune response Co-Ad group: From 1st vaccination up to Month 3	Co-Ad group – Day 1 up to Month 3	PPS
	blood sampling Control group: From 1st vaccination up to Month 5	Control group – Day 1 up to Month 5	
2070*	blood sampling Concomitant infection not related to the vaccine which may influence immune response Comment:	Co-Ad group – Day 1 up to Month 3	PPS
	Co-Ad group: From 1st vaccination up to Month 3 blood sampling Control group: From 1st vaccination up to Month 5 blood sampling	Control group – Day 1 up to Month 5	
2080	Subjects did not comply with vaccination schedule (dates of vaccination not corresponding to adapted protocol intervals provided in SAP or unknown	Co-Ad group: Day 1, Month 2	PPS
	vaccination dates) Comment: Co-Ad group: DOSE 1 – DOSE 2 Control group: DOSE 1 – DOSE 2	Control group: Day 1, Month 2, Month 4	
2090	DOSE 2 – DOSE 3 Subjects did not comply with blood sample schedule (dates of BS not corresponding to adapted protocol	Co-Ad group: Month 1, Month 3	PPS
	intervals provided in SAP or unknown BS/vaccination dates) Comment: Co-Ad group: DOSE 1 – MONTH 1 BS DOSE 2 – MONTH 3 BS Control group: DOSE 1 – MONTH 1 BS DOSE 3 – MONTH 5 BS	Control group: Month 1, Month 5	
2100	Serological results not available post-vaccination (including lost samples, blood sample not done, unable to test, absence of parallelism). Please specify the applicable rule: elimination code if ALL are missing for a subject Comment: Co-Ad group: Check for availability of anti-gE serological result at Month 3 and for pneumococcal serological results at Month 1 Control group: Check for availability of anti-gE	Co-Ad – Month 1, Month 3 Control – Month 1, Month 5	PPS
2120	serological result at Month 5 and for pneumococcal serological results at Month 1 Obvious incoherence or abnormality or error in data	Co-Ad – Month 1, Month	PPS

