204487 (ZOSTER-059 PRI) Statistical Analysis Plan Final

	Statistical Analysis
Code	Condition under which the code is used
2070*	Concomitant infection not related to the vaccine which may influence immune response
	Comment: Up to 30 days post last dose at Visit Month 3 for co-ad group and up to 30 days post last dose at Visit Month 5 for control group
2080	Subjects did not comply with vaccination schedule (dates of vaccination not corresponding to protocol intervals or unknown vaccination dates)
	Comments: Co-Ad group: DOSE 1 – DOSE 2
	Control group: DOSE 1 – DOSE 2
	DOSE 2 – DOSE 3
2090	Subjects did not comply with blood sample schedule (dates of BS not corresponding to adapted protocol intervals or unknown BS/vaccination dates)
	Comments: Co-Ad group: DOSE 1 – MONTH 1 BS
	DOSE 2 – MONTH 3 BS
	Control group: DOSE 1 – MONTH 1 BS
	DOSE 3 – MONTH 5 BS
2100	Serological results not available post-vaccination (including lost samples, blood sample not done, unable to test, absence of parallelism).
	Please specify the applicable rule:
	elimination code if ALL are missing
	Comment:
	Co-Ad group: Check for availability of anti-gE serological result at Month 3 and for pneumococcal serotype at Month 1
	Control group: Check for availability of anti-gE serological result at Month 5 and for pneumococcal serotype at Month 1
2120	Obvious incoherence or abnormality or error in data (incoherence between CRF and results, wrong labelling)
	Comment:
	Co-Ad group: Check for above condition on anti-gE serological result at Month 3 and on pneumococcal serotype at Month 1
	Control group: Check for above condition on anti-gE serological result at Month 5 and on pneumococcal serotype at Month 1
2500	Incomplete vaccination course.
	Comment: The subject should receive one dose of Prevenar 13 vaccine and 2 doses of Hz/su vaccine

BS = Blood sample

^{*} Attribution of these elimcodes are responsibility of CRDL following review of individual data listings

204487 (ZOSTER-059 PRI) Statistical Analysis Plan Final

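### Does the wrong blood sample named under elimination code 2090 put the per-protocol set at risk?

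*SAP*

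**What the plan says.** In SAP Amendment 3, section 5.2.4, code 2090 excludes a subject from the PPS for non-compliance with the blood-sample schedule. The condition covers "dates of BS not corresponding to adapted protocol intervals provided in SAP or unknown BS/vaccination" dates. A comment then lists dose and sample pairs. For Co-Ad the first is Dose 1 with Month 1, and the text goes on: "DOSE 2 – MONTH 1 BS Control group: DOSE 1 – MONTH 1 BS DOSE 3 – MONTH 5 BS". The visit column of that row gives the Co-Ad timepoints as Month 1 and Month 3.

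The intervals themselves are in section 5.1.4. For Co-Ad after the second dose the entry is "HZ/su (Dose 2) – Visit Month 3 for BS", with 28 to 48 days allowed. Template 9 has a Dose 2 to Month 3 column with the same adapted window, and its footnote reads "Adapted = interval used for defining PPS for immunogenicity".

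The three superseded SAP versions show what was intended. Amendment 2 has "DOSE 2 – MONTH 3 BS Control group: DOSE 1 – MONTH 1 BS DOSE 3 – MONTH 5 BS", Amendment 1 has "DOSE 1 – MONTH 1 BS DOSE 2 – MONTH 3 BS Control group: DOSE 1 – MONTH 1 BS", and the April 2018 SAP has "DOSE 2 – MONTH 3 BS". The Amendment 3 entry in the document history opens with "Few templates have been edited for better presentation" and then lists a template removed, a template added and a list of herpes zoster codes. It mentions no change to code 2090.

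**The concern.** The PPS is the primary set for all confirmatory immunogenicity objectives, and code 2090 helps decide who is in it. The Co-Ad sample at Month 3 carries the whole of Family 1 (the vaccine response rate) and the Co-Ad side of Family 2 (the anti-gE GMC ratio). Testing is in fixed sequence, so both families stand before the 13 pneumococcal comparisons.

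Read literally, the comment asks for an interval that cannot exist after Dose 2 and omits the one that matters. A program written from it might check the Dose 3 to Month 5 window in Control but not the corresponding Dose 2 to Month 3 window in Co-Ad. A per-protocol rule applied differently by arm would be unwelcome in an open-label non-inferiority comparison.

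**Working it through.** **1. The printed pair against the SAP's windows.** Count days from Dose 1. Section 5.1.4 allows the Month 1 sample on days 28 to 48 and Co-Ad Dose 2 on days 49 to 83. The printed interval is the Month 1 sample day minus the Dose 2 day.

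- Smallest value: 28 − 83 = −55 days.
- Largest value: 48 − 49 = −1 day.

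With protocol Table 8 (Month 1 at 30 to 42 days, Dose 2 at 49 to 83 days) the range is 30 − 83 = −53 to 42 − 49 = −7 days. The interval is negative throughout, and the SAP gives no window for this pair. The line is therefore a wrong label and cannot be an alternative rule.

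**2. How much of the table is affected.** Section 5.1.4 lists seven intervals, compared here with the comments to codes 2080 and 2090.

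| Interval in 5.1.4 | Code | Repeated correctly |
|---|---|---|
| Co-Ad, Dose 1 to Dose 2 | 2080 | yes |
| Control, Dose 1 to Dose 2 | 2080 | yes |
| Control, Dose 2 to Dose 3 | 2080 | yes |
| Co-Ad, Dose 1 to Month 1 sample | 2090 | yes |
| Co-Ad, Dose 2 to Month 3 sample | 2090 | no (Month 1 printed) |
| Control, Dose 1 to Month 1 sample | 2090 | yes |
| Control, Dose 3 to Month 5 sample | 2090 | yes |

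That is 3 of 3 for code 2080 and 3 of 4 for code 2090, or 6 of 7 in all.

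**3. What the plan yields when followed.** The condition of code 2090 refers the analyst to the intervals in the SAP. Those are in section 5.1.4, which also defines the PPS, and the Co-Ad entry after Dose 2 is Month 3 at 28 to 48 days. Month 3 is also named for Co-Ad in the visit column of the row, in codes 2100 and 2120 for the anti-gE result, in Template 9, and in the primary endpoint (section 4.1). Only the comment disagrees, and it carries no window that could displace the one in 5.1.4.

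**4. What an error in programming would look like.**

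- *Literal use with 28 to 48 days.* The largest possible value is −1, below 28, so every schedule-compliant Co-Ad subject would be eliminated. The group would fall from a planned 410 evaluable subjects to none, which could not pass unnoticed.
- *The Month 3 check is skipped.* Co-Ad subjects sampled outside 28 to 48 days would stay in the PPS. Template 9 counts exactly those subjects in the Exposed Set, Template 47 tabulates eliminations by code, and section 13.1 plans listings of elimination codes and of vaccination and sampling dates. Out-of-window subjects with no code 2090 would show when these are compared. Table 5 of the SAP requires a dry-run review.

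**The case for a change.** The best case for acting is that the comment is the only part of the code 2090 row that pairs doses with samples, so it is what a programmer may look at. Code 2090 also lacks the asterisk that marks codes assigned after a clinical review of individual listings, which suggests that it is set by program. A skipped check is harder to see than it once was. The April 2018 SAP and Amendment 1 ran the Co-Ad interval-deviation table on both the Exposed Set and the PPS; Amendments 2 and 3 run it on the Exposed Set only. Totals will not settle the matter either, because code 2090 also covers the Dose 1 to Month 1 interval. The comparison has to be made subject by subject in the listings.

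Those observations are accurate, and they show that the PPS rule matters. They do not show that the rule is wrong. The harm needs a programmer to set aside the condition of the code, the table in 5.1.4 to which it points, the visit column beside the comment and Template 9. It is also unlikely that the elimination program was written from this line: the three SAP versions before November 2020 printed Month 3, and the Amendment 2 history already mentions a dry-run kick-off meeting. Finally, section 9 commits to an Exposed Set analysis whatever the exclusion rate, so the immunogenicity results will also be seen without this elimination.

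**Conclusion.** This is a clerical slip in one comment, and correcting it gains nothing for the analysis. The rule that decides PPS membership is stated correctly in section 5.1.4, and code 2090 refers to it. Following the plan applies 28 to 48 days to the Co-Ad Month 3 sample, so PPS membership, the vaccine response rate, the GMC ratio and the decisions on the co-primary objectives are not expected to change. Sample size, power and alpha are untouched.

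The conclusion assumes that analysts take windows from 5.1.4, as the condition tells them to. If someone did not, the subjects wrongly kept would be only the Co-Ad subjects whose Month 3 sample fell outside 28 to 48 days. The documents do not allow that number to be estimated.

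One caveat concerns the digit itself. It comes from text converted from PDF, in a table cell broken over several lines, and has not been compared with the signed SAP. If the signed copy prints Month 3, there is no inconsistency at all; if it prints Month 1, the reasoning above stands. Neither case calls for a change to the plan.
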